5.1.5 New York Heart Association classification

The NYHA functional classification will be used to classify the severity of the patients' heart failure ([appendix 10.5](#)). The investigator should place the patients in one of the four categories based on how limited their physical activity are.

Candidates for screening are required to have a NYHA functional class II, III or IV.

The classification of patient's physical activity according to NYHA will be performed at all on-site and if needed, telephone visits until end of the trial.

5.1.6 Clinical Congestion Score

Patient's congestion will be assessed using a clinician-based outcome assessment of 6 different signs and symptoms: dyspnea, orthopnea, fatigue, jugular venous distention (JVD) (as assessed by the investigator), rales, and edema. Each category will be assessed through a four-measure questionnaire which will be further converted to a standardized 4-point scale ranging from 0 to 3 as shown in [table 5.1.6:1](#).

Table 5.1.6:1 Clinical congestion score

Signs/Symptoms	0	1	2	3
Dyspnea	None	Seldom	Frequent	Continuous
Orthopnea	None	Seldom	Frequent	Continuous
Fatigue	None	Seldom	Frequent	Continuous
JVD (cm H ₂ O) (jugular venous distension)	≤6	6 < JVD < 10	10 ≤ JVD < 15	≥15
Rales	None	Bases	From base to <50%	From base to >50%
Edema	Absent/ trace	Slight	Moderate	Marked

The Clinical Congestion Score will be completed according to the [Flow Chart](#). Please refer to [section 6.2.2](#) for preferred order of completion of assessments.

5.1.7 Patient Global Impression of Change in Heart Failure Symptoms

! "# Patient %&'(%)*+,#--.&/ &01 "(/2# ./ 3#(,4 5(,%6,#78*+4&*-. - (9: 4#* ;6#-4.&/(.,# 4& (-#-- +(4.#/4<- .*+,#--.&/ &0 ="(/2# ./ "#(,4 0(,%6,# -8*+4&*-> -+#=.0=(%%8? -"&,4/#-- &0,#(4"> 0(4.26#(/@ -A#%%./2B

The PGI-C asks the patient to choose one response that best describes the overall change (if any) in his/her Heart Failure Symptoms, specifically: shortness of breath, fatigue and swelling since he/she started taking the trial medication &/ 4"# 0&%%&A:≠(C#2&,8=(%#?

- Very much better (+3)
- Much better (+2)
- A little better (+1)
- No change (0)
- A little worse (-1)
- Much worse (-2)
- Very much worse (-3)

Please refer to [section 6.2.2](#) for order of completion of patient reported outcome measures and [appendix 10.3.3](#).

5.1.8 Patient Global Impression of Change in Dyspnea

The Patient Global Impression of Change in dyspnea is a 1-item questionnaire designed to assess the patient's impression of change in dyspnea.

The PGI-C asks the patient to choose one response that best describes the change (if any) in his/her shortness of breath when performing usual activities since he/she started taking the trial medication on the following 7-category scale:

- Very much better (+3)
- Much better (+2)
- A little better (+1)
- No change (0)
- A little worse (-1)
- Much worse (-2)
- Very much worse (-3)

Please refer to [section 6.2.2](#) for order of completion of patient reported outcome measures and [appendix 10.3.4](#).

5.1.9 Patient Global Impression of Severity of Heart Failure Symptoms

Patient Global Impression of Severity of Heart Failure Symptoms .- (9: .4##* ;6#-4.&/(.,# 4& (-#-- +(4.#/4<- .*+,#--.&/ &0 -8*+4&*- -#D#, .48>+#= .0.=(%%%8&,4/#-- &0,#(4"> 0(4.26# (/@ -A#%%%/2B

The PGI-S asks the patient to choose one response that best describes how his/her Heart Failure Symptoms, specifically: shortness of breath, fatigue and swelling are now on a 5-point scale:

- Not at all (1)
- Mild (2)
- Moderate (3)
- Severe (4)
- Very severe (5)

Please refer to [section 6.2.2](#) for order of completion of patient reported outcome measure and [appendix 10.3.5](#).

5.1.10 Patient Global Impression of Severity of Dyspnea

Patient Global Impression of Severity of Dyspnea is a 1-item questionnaire designed to assess patient's impression of symptom severity, specifically dyspnea.

The PGI-S item asks the patient to choose one response that best describes how his/her dyspnea is now on a 5-point scale:

- Not at all (1)

- Mild (2)
- Moderate (3)
- Severe (4)
- Very severe (5)

Please refer to [section 6.2.2](#) for order of completion of patient reported outcome measures and [appendix 10.3.6](#).

5.1.11 Clinician Global Impression of Change in CHF Severity

Clinician Global Impression of Change in CHF Severity is a 1-item questionnaire designed to assess Investigator's (physician's) overall impression of change in the patient's chronic heart failure severity related to his/her participation in the study; specifically signs and symptoms associated with chronic heart failure on a 7-point scale.

This questionnaire is assessing change from baseline. For consistency, the same Investigator should assess the patient at each visit. If this is not possible, then the response 'N/A = cannot be assessed' should be selected.

- N/A = Cannot be assessed
- 1 = Very much improved
- 2 = Much improved
- 3 = Minimally improved
- 4 = No change
- 5 = Minimally worse
- 6 = Much worse
- 7 = Very much worse

Please refer to [section 6.2.2](#) for preferred order of completion of assessments and [appendix 10.4.1](#).

5.1.12 Clinician Global Impression of Severity of CHF

Clinician Global Impression of Severity of CHF is a 1-item questionnaire designed to assess Investigator's overall impression of severity of chronic heart failure, specifically signs and symptoms associated with chronic heart failure now (at the time-point of assessment) on the 5-point scale:

- Normal, not at all ill (1)
- Mildly ill (2)
- Moderately ill (3)
- Severely ill (4)
- Very severely ill (5)

Please refer to [section 6.2.2](#) for preferred order of completion of assessments and [appendix 10.4.2](#).

5.2 ASSESSMENT OF SAFETY

5.2.1 Physical examination

A complete physical examination will be performed at the time points specified in the [Flow Chart](#). Complete physical examination will include general appearance as well as evaluation of organ systems including an assessment of the cardiovascular system.

The results must be included in the source documents available at the site.

5.2.2 Vital signs

Vital signs will be evaluated at the time points specified in the [Flow Chart](#). This includes systolic and diastolic blood pressure and pulse rate (electronically or by palpation count for 1 minute) in a seated position after 5 minutes of rest.

All recordings should be made using a similar type of and validated certified blood pressure recording instrument on the same arm. Further details on blood pressure measurement procedure are provided [appendix 10.6](#).

5.2.3 Body weight and height

Measurements of body weight and height will be performed at the time points specified in the [Flow Chart](#).

Body Mass Index (BMI) (kg/m²) will be calculated for determination of eligibility at Visit 1.

Body weight should be measured as follows:

- after the urine sampling (weight after bladder voiding),
- shoes and coat/jackets should be taken off, and
- pockets should be emptied of heavy objects (i.e. keys, coins etc.).

5.2.4 Safety laboratory parameters

Safety laboratory parameters to be assessed are listed in [table 5.2.4.1](#). For the sampling time points please see the [Flow Chart](#).

All analyses will be performed by a central laboratory, the respective reference ranges will be provided in the ISF.

Patients do not have to be fasted for the blood sampling for the safety laboratory. Instructions regarding sample collection, sample handling/ processing and sample shipping are provided in the Laboratory Manual in the ISF.

The central laboratory will send reports to the investigator. It is the responsibility of the investigator to evaluate the laboratory reports. Clinically relevant abnormal findings as judged by the investigator will be reported as adverse events (please refer to [section 5.2.7.1](#)).

In case the criteria for hepatic injury are fulfilled, a number of additional measures will be performed (please see [section 5.2.7.1](#) and the DILI Checklist provided in the ISF and electronic data capture (eDC) system. The amount of blood taken from the patient concerned will be increased due to this additional sampling.

The central laboratory will transfer the results of the analysis to the sponsor.

Table 5.2.4:1 Safety laboratory tests

Haematology

• Hematocrit• Haemoglobin
- Reticulocyte Count (reflex test if Hb outside normal range)• Red Blood Cells (RBC) / Erythrocytes• WBC / Leukocytes• Platelet Count / Thrombocytes• Differential Automatic (relative and absolute count): Neutrophils, Eosinophils, Basophils, Monocytes, Lymphocytes
Clinical chemistry

• Albumin• Alkaline phosphatase
- γ-GT (gamma-glutamyl transferase) reflex test triggered by elevated alkaline phosphatase on two sequential measures• ALT (alanine transaminase, SGPT)• AST (aspartate transaminase, SGOT)• Bicarbonate• Bilirubin total, fractionated if increased• Chloride• Creatinine• Creatine kinase (CK)• Hs Troponin I (reflex tests if CK is elevated)• Glucose• Potassium• Protein total

• Sodium• Urea (BUN)• Uric acid
Urine

• Urinalysis: standard dipstick test including ketones semi-quantitative measurement

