1.2 DRUG PROFILE

Empagliflozin is an orally available, potent, and selective inhibitor of the renal SGLT-2. Its selective inhibition reduces renal reabsorption of sodium and glucose. This leads to both increased urinary sodium and glucose excretion. While urinary sodium excretion returns to normal within few days of empagliflozin administration, the effect on urinary glucose continues for as long as the medication is used.

Empagliflozin has been developed for the treatment of T2DM, and has received marketing approval in various regions including for example the European Union, Latin American countries, USA and Japan where it is marketed under the brand name Jardiance®.

For a more detailed description of the drug profile please refer to the current Investigator’s Brochure (IB) [[c01678844-09](#)] and local prescribing information for empagliflozin.

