4.1.5 Blinding and procedures for unblinding

4.1.5.1 Blinding

Patients, investigators and everyone involved in trial conduct or analysis or with any other interest in this double-blind trial will remain blinded with regard to the randomised treatment assignments until after database lock.

The DMC will be provided with unblinded data in order to allow them to review efficacy and safety and to fulfil their tasks as outlined in the data monitoring committee charter. An independent team, not otherwise involved in the conduct of the trial, will provide the unblinded results to the DMC.

The randomization code will be kept secret by Clinical Trial Support up to database lock.

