7.7 DETERMINATION OF SAMPLE SIZE

In clinical studies, 30-50 meters have been variably reported as a meaningful distance achieved as a result of therapy [[R17-1227](#)].

The standard deviation (SD) of 72 m is assumed for sample size considerations of this trial [[R17-1225](#)]. The risk of observing a higher SD in this trial will be mitigated by using duplicate measurements of 6MWT at baseline, Week 6 and Week 12 [[R17-2791](#)]. For non-missing values a normal distribution for change from baseline in distance walked in 6 minutes is assumed in all below sample size estimations.

The trial is designed to achieve a power of 90% for a two sided test at level $\alpha = 0.05$ to detect a difference between empagliflozin and placebo.

Using a normal distribution to calculate the probability that an observation X in Empagliflozin group will be less than an observation Y in the control group under the alternative, the following table presents the number of required evaluable patients for different assumed means of absolute difference in distance walked within 6 minutes as obtained by using the Wilcoxon sample size estimation procedure from commercial software nQuery Advisor® 7.0 statistical package by Statistical Solutions Ltd.

Table 7.7: 1 Sample size calculation

True treatment difference in distance walked in 6 minutes	SD	P(X<Y)	Required number of patients per group
30 m	72 m	0.384	131
40 m	72 m	0.347	76
50 m	72 m	0.312	50

A true treatment difference of 30 m is used as a conservative measure for sample size calculation to ensure that the study could detect the lowest effect size reported to be meaningful.

Therefore, a total of 131 evaluable patients per group are needed in order show a significant result for a two-sided test at level $\alpha = 0.05$ with a power of 90% not considering missing data.

To assess the impact of missing data a simulation with 100000 iterations was performed. A normal distribution for 6MWT distance was assumed and a total of 5%, 8% and 10% patients imputed to worst case as outlined in [section 7.5](#) in each treatment group were investigated. The results are summarized in [table 7.7: 2](#).

Table 7.7: 2 Simulation of imputation rules

N per group	Simulated true treatment difference for non-missing data [mean \pm SD]	Percentage of missing data imputed to worst case	Power
150	30 \pm 72	5%	90%
150	30 \pm 72	8%	87%
150	30 \pm 72	10%	85%

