10. HISTORY TABLE

This is a revised TSAP including the following modifications to the final TSAP

Table 10: 1 History table

| Version | Date (DD- MMM-YY) | Author | Sections changed | Brief description of change |
|---------|----------------------|--------|---|--|
| FINAL | 5-APR-19 | | None | This is the final TSAP |
| REVISED | 21-OCT-19 | | Section 6.3 / Section 7.4 / Section 7.5 | 
Definition of Sensitivity analysis set 2 and Sensitivity analysis set 3
 
Reason for change: For a subset of patients, on-treatment urine dipstick test results for urine glucose had been transferred from the central laboratory to the sites before DBL. A positive urine glucose test can be suggestive of treatment allocation. Therefore, an additional sensitivity analysis is performed based on the subset of patients who did not have an on-treatment urine glucose measurement transferred to and accessed by the sites before DBL.
 
In patients with diabetes mellitus at baseline, a positive urine dipstick test result is of limited value with respect to bearing potential information on treatment allocation. Therefore, a second additional sensitivity analysis is performed, which excludes those non-diabetic patients for whom at least one on-treatment urine glucose measurement was transferred to and accessed by the sites before DBL.
 |
| | | | Section 6.4. | 
Importance of subgroup diabetic vs non diabetic highlighted.
 
Reason for change: Clarification.
 
Categorisation of subgroup eGFR at baseline updated
 
Reason for change: Combine subgroups to avoid small subgroup
 |

Table 10: 1 History table (cont.)

| Version | Date (DD- MMM-YY) | Author | Sections changed | Brief description of change |
|---------|----------------------|--------|------------------|--|
| | | | Section 6.6 | 
Clarification of 6MWTD if a patient performs the visit at week 12 but does not perform the 6MWT.
 
Clarification of handling of missing baseline questionnaires for WCI analyses.
 
Clarification of handling of SAE with outcome “recovered with sequelae” leading to an amputation
 
Reason for change: Clarifications consistent with protocol.
 |

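### The protocol nowhere withholds urine glucose from site laboratory reports, so a Week 6 dipstick result can suggest allocation before the Week 12 walk test

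*Protocol*

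**What the plan says.** **What is measured and who sees it.** Protocol Table 5.2.4:1 gives the urine test as "Urinalysis: standard dipstick test including ketones semi-quantitative measurement". The Flow Chart places urinalysis at every visit, including Visit 3 (Week 6, on treatment). Its footnote 4 shortens only the blood panel at Visit 3. Section 5.2.4 continues: "The central laboratory will send reports to the investigator". The investigator has to evaluate these reports, and the results also go to the sponsor.

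**What the drug does.** Section 1.2 says that "the effect on urinary glucose continues for as long as the medication is used". Section 4.1.2 puts glucose loss in healthy volunteers at roughly 50 g a day on either dose, so the effect does not depend on diabetes.

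**What blinding requires.** Under section 4.1.5.1, patients, investigators and all others involved "will remain blinded with regard to the randomised treatment assignments until after database lock". That section covers the randomisation code and the route by which an independent team supplies the DMC. It does not mention laboratory values that could reveal treatment.

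**What the SAP records.** The history table (SAP section 10) states that on-treatment urine glucose results reached sites before database lock for a subset of patients. It adds: "A positive urine glucose test can be suggestive of treatment allocation". It regards the result as much less informative in patients with diabetes. SAP 6.3 therefore defines SensRS2, which drops every patient with a released and accessed result, and SensRS3, which drops only the non-diabetic ones. Sections 7.4.2 and 7.5.1.2 repeat the primary and key secondary analyses on these sets.

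**The concern.** Three statements in the protocol do not fit together: a persistent pharmacological marker in urine, a dipstick report that goes to the site, and a promise that the site stays blinded. Nothing removes the marker from the report.

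The outcomes exposed are sensitive to expectation. The protocol itself describes the 6MWT as self-paced (section 3.2). Both key secondary endpoints are patient-reported. The Clinical Congestion Score and the clinician global impressions are rated by the investigator, who is the person receiving the report. A site that reads a positive Week 6 result in a patient without diabetes has a reason to guess empagliflozin about six weeks before the primary measurement.

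The SAP response comes after the event. The primary analysis stays on all randomised patients, and no rule says what follows if SensRS2 or SensRS3 disagrees with it. The sets are keyed to access before database lock, not to access before the patient's own Week 12 test. SAP Table 6.2:1 has a deviation code for inappropriate code breaks (C4.01) but none for this disclosure.

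**Working it through.** **1. Can a report precede the primary measurement?** Protocol 6.2.2 puts patient-reported outcomes first, then examination, clinician scales, ECG and 6MWT, and lists the laboratory sample last as the preferred order. At Week 12 the sample therefore follows the outcomes it might influence. At Week 6 there is no earlier scheduled on-treatment sample. For a patient on schedule, one report matters: Week 6, readable before Week 12. A patient who stops early also has a sample at the early discontinuation visit, before any later Week 12 visit.

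**2. Reproduce the plan's figures.** Inputs from protocol 7.7: SD 72 m, two-sided alpha 0.05, power 90%, and "A true treatment difference of 30 m is used as a conservative measure for sample size calculation".

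- P(X<Y) = Phi(-30/(72 x sqrt 2)) = Phi(-0.295) = 0.384.
- n per group = (1.960 + 1.282)^2 / [6 x (0.384 - 0.5)^2], with P unrounded = 131, as in Table 7.7:1. The 40 m and 50 m rows give 76 and 50, also as stated.
- Simulated Wilcoxon power at 150 per group, with equal fixed numbers ranked worst in each arm: 90% (7 or 8 missing), 87% (12) and 85% (15), as in Table 7.7:2. If missingness is drawn at random instead, power is 89%, 84% and 81%.

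The model used below therefore matches the plan's own.

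**3. Illustrative effect on type I error.** Assumptions, none of them in the documents: no true effect; a mean gain of b metres in a share f of the empagliflozin arm only; 150 per group; 5% missing at random. The range f = 55-75% is 100% minus the 25-45% type 2 diabetes share that section 1.1 gives for heart failure generally. Two-sided rejection rates:

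| Share affected | b = 5 m | b = 10 m | b = 15 m |
|---|---|---|---|
| 10% | 5.1% | 5.0% | 5.4% |
| 25% | 5.1% | 5.5% | 6.8% |
| 55% | 5.9% | 8.9% | 14.0% |
| 75% | 6.7% | 12.4% | 22.0% |

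With 8 missing fixed in each arm, the 10 m column reads 4.1%, 6.9% and 9.9% for 25%, 55% and 75%. If placebo patients also lost 10 m, the random-missing figures for 55% and 75% would be 21% and 36%. The answer depends almost wholly on inputs that the documents do not supply.

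**4. What the sensitivity sets can show.** Power at 30 m and SD 72 m, about 5% missing, with exclusions assumed equal in both arms:

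| Excluded | n per group | Power |
|---|---|---|
| 0% | 150 | 90% |
| 10% | 135 | 87% |
| 25% | 112 | 79% |
| 40% | 90 | 71% |
| 55% | 68 | 58% |
| 75% | 38 | 33% |

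If few patients are excluded, the repeat is informative. If many are, a non-significant repeat cannot separate bias from loss of power. The SAP gives no count, so it is not known which case applies.

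**The case against.** The best defence is that the protocol is silent, not permissive. Table 5.2.4:1 names ketones and not glucose, section 4.1.5.1 commits to the blind, and the Laboratory Manual, which is not among the documents, may already have masked glucose. The SAP's reference to a subset fits an execution failure at least as well as a plan that released every result. This stands as far as it goes, so it cannot be said that the protocol orders unmasked reporting. But the SAP confirms that the dipstick measured glucose and that results reached sites. Any masking rule kept elsewhere did not hold for those patients.

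The safeguards are also real. Encouragement during the walk is scripted, with other words and body language barred (Appendix 10.1.4). The KCCQ is completed with the patient left alone (section 5.1.2). Reports go to the investigator, and nothing provides for passing them to patients. This weakens the route to the patient-reported outcomes and narrows the route to the walk. It does little for the investigator-rated scales.

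Finally, the SAP does respond: SensRS2, SensRS3 and the emphasis on the diabetes subgroup (SAP 6.4) are sensible ways to look at impact. They assess it; they do not prevent it.

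**Conclusion.** The gap holds. Followed as written, section 5.2.4 lets a result that can suggest treatment reach sites before the Week 12 outcomes, and the SAP records that this happened for some patients.

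Three stronger readings are tempting, and the documents do not support them.

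- A reader might infer that the dipstick all but identifies treatment in non-diabetic patients. The SAP says only that it can be suggestive, and neither document gives its accuracy in a population that admits eGFR down to 20.
- A reader might infer that 165-225 patients (55-75% of 300) were unblinded. That requires release and reading of every non-diabetic patient's result, whereas the SAP says a subset. The diabetes share is general background, and SAP 9.2 also counts HbA1c of 6.5% or more as diabetes, which may shrink the non-diabetic group.
- A reader might infer a bias in favour of the drug of a stated number of metres. Neither size nor direction can be derived from the documents.

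The defensible range is conditional: type I error near 5% if about 10% of patients were affected and the gain was at most 15 m, and about 9-12% with full release in 55-75% of patients and a 10 m gain in the empagliflozin arm only. It rests on the assumptions in step 3 of the working.

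**What to change.** 1. State in section 5.2.4 and Table 5.2.4:1, in section 4.1.5.1 and in the Laboratory Manual that urine glucose is suppressed from every post-randomisation report visible to sites or to the blinded sponsor team until database lock. It is available only to the independent unblinded team and the DMC, a route that section 4.1.5.1 already sets up. Ketones and all other urinalysis results continue to be reported.
2. This cannot undo results already released. For those, report by arm and by diabetes status how many patients had a urine glucose result accessed before their own Week 12 6MWT, and place this beside SensRS2 and SensRS3 so that their reach and power can be judged.

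Cost: a central laboratory report setting, matching text in three places and one small table. There are no extra visits or tests, and the 131 evaluable and 150 randomised patients per group are unchanged.
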